#### **Section 3: Trial methods**

## Trial design

The VITaCCA trial is a double-blind, multicenter, randomized placebo-controlled trial with a three-arm comparative design. Patients are randomized to one of 3 treatment groups. Group 1 will be treated with placebo (0.9% NaCl), group 2 with a twice-daily intravenous bolus of 1.5g vitamin C and group 3 with a twice-daily intravenous bolus of 5g vitamin C for 4 days or until ICU discharge. In addition, all patients receive intravenous thiamine 200 mg every 12h for 4 days or until ICU discharge.

The clinical trial has been conducted in six Dutch ICUs: Amsterdam UMC, location VUmc (coordinating center), Erasmus MC, Amphia Hospital, OLVG, location East, Maasstad Hospital and Gelderse Vallei Hospital.

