#### Timing of outcome assessments

Detailed information about timing of the outcome assessments can be found in the methods section of the trial protocol paper [1].

When patients were discharged early, i.e. during the first 4 days of ICU-admission, data was also collected on the day of discharge except for diuresis and fluid balance as these do not reflect a full 24 h period of time. Data was not collected on the ward after ICU-discharge.

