## Adherence and protocol deviations

Information regarding adherence to the study intervention is collected in Castor for each patient, most importantly 'first dose <5 hours after ROSC' and 'total doses of study medication administered'. All protocol deviations will be noted on a protocol deviation form and shared with the coordinating center. Analysis will be performed according to the intention-to-treat principle, see later.

The study procedures were terminated when a patient did not fulfill all inclusion criteria and/or when a patient suddenly fulfilled one of the 3 upper safety exclusion criteria (see section 5 for study criteria), when more information became available after the study had already been started (after at least one dose of study medication). Deferred consent was asked in all cases in order to follow-up every randomized and treated patient.

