#### 'Modified intention-to-treat analysis' (mITT) – Primary analysis

- All randomized and treated patients
  - Without patients who received the first dose with a delay (>5 hours after ROSC).
  - Without patients who turned out not to be eligible (not fulfilling all inclusion criteria).
- For this analysis the trial is powered: 270 patients, 90 in each arm.

For clarification: treated patients who met the inclusion criteria but suddenly fulfilled one of the 3 upper safety exclusion criteria were also included in the primary mITT analysis, but further administration of study medication was terminated.

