#### A flow diagram of all randomized patients is constructed, including:

- Number of randomized patients in whom the study was eventually not initiated, with reason
- Number of randomized patients in whom study treatment A, B or C was initiated
- Number of excluded patients, with reason
- Number of patients in each arm included in the ITT-analysis
- Number of patients in each arm included in the mITT-analysis
- Number of patients (in ITT- and mITT-analysis) in whom study treatment was discontinued, with reason

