#### Follow-up

There are two main reasons for lost to follow up:

- Included patients who are transferred to an ICU or ward of another hospital. Primary endpoint data (to calculate SOFA T96 h) will be collected from the hospitals involved (with consent). Other secondary endpoints will be missing, except for the questionnaires at day 28 and day 180.
- Included patients or their relatives who are not reachable by phone for questionnaires at day 28 and day 180.

The amount and timing of patients lost to follow up will be mentioned in the manuscript or supplementary file.

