#### Planned sensitivity analyses

Two sensitivity analyses will be carried out:

- Excluding randomized patients who died <96 hours because death at 96h was counted
  as the maximum R-SOFA score of 24 points. The choice to give 24 points to deceased
  patients may have a large impact on the primary analysis.

- Excluding randomized patients from whom the study treatment was terminated prematurely (<96 hours). For instance, this applies to patients transferred from ICU to ICU during the study period and patients fulfilling one of the 3 safety exclusion criteria.

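### Does the second sensitivity analysis throw out patients who left the ICU alive before 96 hours?

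*SAP*

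**What the plan says.** Under Trial design, the SAP gives study medication "for 4 days or until ICU discharge", so leaving the ICU is one of two planned ends of treatment. Timing of outcome assessments foresees that some patients leave within the first four days.

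Under Planned sensitivity analyses there are two exclusions. The first removes patients who died before 96 hours, because death is scored at the maximum of 24 points. The second is worded "Excluding randomized patients from whom the study treatment was terminated prematurely (<96 hours" and goes on: "For instance, this applies to patients transferred from ICU to ICU during the study period", with patients who meet a safety exclusion criterion as the other example.

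The same verb appears in two other places. Adherence and protocol deviations has "The study procedures were terminated when a patient did not fulfill all inclusion criteria", together with patients who come to meet a safety criterion. The definition of the modified intention-to-treat set says of those safety patients that "further administration of study medication was terminated". The flow diagram is to show the number of patients "in whom study treatment was discontinued, with reason".

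**The concern.** The only operational figure in the second exclusion is 96 hours, and every patient discharged alive from the ICU before then has treatment that ended inside that limit. The examples are introduced as instances, so they do not close the list, and no sentence expressly exempts planned discharge. One programmer could work from the number of doses given and drop these patients; another could work from the recorded reason for stopping and keep them.

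The choice matters in principle. Early live discharge happens after randomization and plausibly goes with a low R-SOFA. If vitamin C speeds recovery, a purely time-based exclusion removes more good outcomes from the vitamin C arms than from placebo. An analysis meant to test the primary result could then make a real benefit look fragile.

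**Working it through.** **What the text supports**

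1. The criterion is treatment that ended prematurely, with 96 hours in brackets as a gloss. Treatment that ends at a planned end point is not premature. Trial design makes ICU discharge such a point, so these patients meet the bracket but not the whole criterion.
2. Both examples are unplanned stops: a transfer that interrupts treatment in a patient who still needs intensive care, and a safety criterion that comes to light later.
3. The transfer example is confined to moves between ICUs. When the SAP means a wider group it says so, as under Follow-up: "Included patients who are transferred to an ICU or ward of another hospital". If every end before 96 hours counted, the narrower example would be an odd choice.
4. The two other uses of the verb quoted above concern eligibility and safety stops, not recovery.
5. If time alone decided, patients who died before 96 hours would also drop out of the second analysis, and the first exclusion would be nested in it. The SAP lists the two side by side as different checks, which fits a time-only rule poorly.

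**What the time-only reading would do**

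The SAP gives no SD, mean score, death rate or early-discharge rate, so this is conditional throughout.

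*SD.* From Sample size: 82 per group, difference 2, power 90%, two-sided alpha 0.01. With n = 2(z₀.₉₉₅ + z₀.₉₀)²·SD²/δ² and z-sum 2.576 + 1.282 = 3.857, SD² = 82 × 4 / (2 × 14.88) = 11.02, so SD ≈ 3.32. This is implied, not stated.

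*Model.* Assume survivors' 96-hour scores are N(8, 3.3) on placebo and N(6, 3.3) on vitamin C, a true difference of -2.00, with 12% early deaths per arm. Early live discharge is logistic in the score with a common intercept, set so that 5, 10, 20 or 30% of all placebo patients leave early. Deaths are left out of the comparison, since a time-only rule would remove them too. Numerical integration gives the difference among those who remain:

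| Log-odds slope per point | 5% | 10% | 20% | 30% |
|---|---|---|---|---|
| 0 | -2.00 | -2.00 | -2.00 | -2.00 |
| -0.1 | -1.99 | -1.98 | -1.96 | -1.95 |
| -0.25 | -1.92 | -1.87 | -1.80 | -1.76 |
| -0.5 | -1.76 | -1.65 | -1.50 | -1.42 |

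The largest shift is 2.00 - 1.42 = 0.58 points; at slope -0.1 it is at most 0.05. At 20% early discharge on placebo and 90 per arm, the time-only rule removes 90 × 0.20 = 18 placebo patients and about 21, 25 or 29 per vitamin C arm at slopes -0.1, -0.25 and -0.5.

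*Second model.* Take scores N(0, 3.32) against N(-2, 3.32), with discharge when a severity variable correlated ρ with the score falls below a threshold t. The mean of those who stay is μ + ρ·SD·φ(a)/(1 - Φ(a)), where a = t - ρμ/SD. For ρ = 0.5 and 20% on placebo, t = -0.842. Placebo: 0.5 × 3.32 × 0.350 = 0.58. Active: a = -0.540 and -2 + 1.66 × 0.489 = -1.19. The difference is -1.19 - 0.58 = -1.77. Over ρ from 0.3 to 0.8 and 10 to 30% early discharge, it runs from -1.94 to -1.27.

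Both models agree on direction. Neither can say how large the shift would be in this trial, and both use raw 96-hour scores, whereas the SAP models the change score with adjustment for baseline and age.

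**The case for a change.** The best case for a change is that likely intent does not fix a population. The bracket explains the term by elapsed time, not by departure from the planned course; the list of examples is open; and the SAP itself defines this analysis, so the gap is not one it hands to the protocol. Transfer to another ICU is also, in a sense, leaving the study ICU, so one kind of departure already counts. A single clause would settle the matter, and could also say whether early deaths stay in.

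Part of this stands: the SAP does not spell out how planned discharge, or death, before 96 hours is classified here. But that is detail left unwritten, not a contradiction. The sensible reading is also the natural one, and the reasons for discontinuation needed to apply it are collected for the flow diagram in any case. The SAP also has the analyses run first with the arms coded A, B and C, which limits the scope for choosing a classification to suit a result.

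A related question is which score serves at 96 hours for patients already on the ward, given that "Data was not collected on the ward after ICU-discharge". It does not strengthen the case: the SAP refers the details of the primary outcome to the published protocol, which is not at hand.

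**Conclusion.** No change to the plan follows. The 96-hour figure, taken alone, would sweep in patients discharged alive as planned. The full criterion, its examples and the SAP's own use of the verb point to unplanned stops only. This is a gap that a competent analyst would most likely fill correctly.

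If it were filled the other way, one of two sensitivity analyses would be affected and the primary analysis would not. The estimate would move towards no effect, so the error could not create a false benefit. On the assumed inputs the shift is 0 to 0.58 points in the logistic model and 0.06 to 0.73 in the threshold model (2.00 - 1.94 and 2.00 - 1.27). These sizes rest on assumed early-discharge rates and an assumed link between discharge and score, neither of which the SAP supplies; only the direction is informative.

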#### Subgroup analyses

In order to evaluate possible effect modification, in additional analyses, age and first measured pH will be added to the model including the interaction with the intervention variable. When the interaction term is statistically significant, results will be reported for relevant subgroups.

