#### Randomization

Eligible patients will be randomized using a computer-generated randomization list in a 1:1:1 ratio to one of the three treatment groups. Randomization will be stratified by site and age ( $\leq$ 66 and  $\geq$ 66 years) in blocks of 6. Patients were randomized only if early administration of the first dose ( $\leq$ 5 hours after ROSC) was still feasible. Deferred informed consent was obtained  $\leq$ 72 hours after inclusion/randomization.

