#### Sample size

Eighty-two patients per group are needed to detect a treatment effect of 2 SOFA points with 90% power and a two-sided alpha of 0.01 [1]. The study aimed to include 3x 90 patients to compensate for 10% loss after randomization for late outcomes.

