# **Section 4: Statistical principles**

#### **Confidence intervals**

Effect estimates will be reported with confidence intervals. The confidence intervals will be 95% and two-sided.

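### Subgroup results for age and first pH are promised only if the interaction is significant, so what readers see depends on the p-value

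*SAP*

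**What the plan says.** Under Subgroup analyses (Section 6), the SAP plans additional models in which "age and first measured pH will be added to the model including the interaction with the intervention variable". The next sentence is the section's only statement on reporting: "When the interaction term is statistically significant, results will be reported for relevant subgroups".

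Three things that this rule depends on are not fixed there:

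- **Significance level.** None is given for the interaction. The Sample size section works "with 90% power and a two-sided alpha of 0.01", while the Confidence intervals section sets 95% intervals.
- **Form of the test.** Patients are allocated by a "computer-generated randomization list in a 1:1:1 ratio to one of the three treatment groups", so each modifier carries two dose-by-modifier terms. The section speaks of the interaction term in the singular and does not say whether it is tested jointly or dose by dose.
- **Subgroups.** Which subgroups count as relevant is not defined. Age has a natural cut at 66 years from the stratification. First pH has neither a cut nor a stated scale.

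The nearest general commitment is in Section 4, Confidence intervals: "Effect estimates will be reported with confidence intervals". It does not mention interactions that are not significant.

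**The concern.** Two modifiers were chosen in advance, so two answers are owed. As written, an answer is promised only when it is statistically significant. This matters in two ways.

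First, the trial is sized for a main effect and has limited power for interactions. An interaction that clears the threshold will on average overstate the true one. Readers and later meta-analyses would meet the contrast mainly when it is extreme.

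Second, a non-significant interaction with a wide interval tells the reader that the trial could not exclude effect modification. If nothing is shown, the reader may take it as evidence of none. For pH, the cut could also be chosen after the interaction has been seen.

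**Working it through.** **Inputs.** "Eighty-two patients per group are needed to detect a treatment effect of 2 SOFA points", "with 90% power and a two-sided alpha of 0.01" (Sample size); "For this analysis the trial is powered: 270 patients, 90 in each arm" (definition of the mITT population). The SAP gives no SD and no interaction alpha. The assumptions are alpha 0.05, a modifier that splits patients into two halves, and one dose compared with placebo.

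**Step 1: the plan's own figure.** Without an SD, 82 per group cannot be reproduced independently, but it can be inverted:

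SD = 2 × √(82/2) / (2.576 + 1.282) = 12.81 / 3.86 = 3.32.

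In the forward direction, SD 3.3 gives 2 × (3.857)² × 3.3² / 2² = 81.0, for which the sample-size routine returns 82. A t-test version implies 3.29. So about 3.3 is the design SD.

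**Step 2: smallest significant interaction.** For the difference between two subgroup effects, with n per arm and fraction f in one subgroup:

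SE = SD × √(2/(n·f) + 2/(n·(1−f))) = 3.32 × √(2/45 + 2/45) = 0.99.

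Threshold = 1.96 × 0.99 = 1.94 points, close to the whole 2-point design effect.

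**Step 3: how often the filter is passed, and with what estimate.** The probability of significance is 1 − Φ(1.96 − d/SE) + Φ(−1.96 − d/SE) for a true interaction d. The mean absolute estimate given significance is from two million normal draws.

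| SD | Split | Alpha | True d | P(significant) | Mean absolute estimate if significant |
|---|---|---|---|---|---|
| 3.32 | 50/50 | 0.05 | 0 | 5% | 2.32 |
| 3.32 | 50/50 | 0.05 | 1 | 17% | 2.47 |
| 3.32 | 50/50 | 0.05 | 2 | 52% | 2.75 |
| 3.32 | 30/70 | 0.05 | 2 | 46% | 2.94 |
| 3.32 | 50/50 | 0.01 | 2 | 29% | 3.17 |
| 5 | 50/50 | 0.05 | 2 | 27% | 3.83 |
| 7 | 50/50 | 0.05 | 2 | 16% | 5.18 |

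The larger SDs are shown because the primary outcome scores a death before 96 h as 24 points (Planned sensitivity analyses), which may widen the spread beyond the design value.

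**Step 4: the three-arm joint test.** If both doses share the same true interaction, a joint 2-df test at 0.05 with SD 3.32 has simulated power of 17% at 1 point and 54% at 2 points. The picture is the same as for a single dose.

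**Step 5: continuous pH.** If pH is roughly normal and enters linearly, the contrast between the averages of the upper and lower halves spans about 1.6 pH SDs. Its SE is then 3.32 × √(2/90) × 1.6 = 0.79, and the threshold is 1.96 × 0.79 = 1.55 points. A continuous term lowers the threshold but does not remove the selection.

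**Step 6: false positives when no interaction exists.**

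- One 2-df test per modifier: 1 − 0.95² = 9.8%, treating the two modifiers as independent.
- Each dose term tested separately: the two contrasts share the placebo arm (correlation 0.5), which gives about 9.1% per modifier. Over two modifiers, 1 − (1 − 0.091)² is about 17%.

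**The case against.** The strongest reply is that the rule is a recognised safeguard. Showing stratum-specific effects only after an interaction test discourages readers from comparing separate subgroup p-values. Both modifiers are named in advance, the analyses are called additional, and the SAP promises intervals with effect estimates in general. All of that stands. It supports caution with stratum-specific effects, but it does not require leaving the interaction estimate itself to depend on its p-value.

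Three stronger readings are tempting, and the SAP does not support them:

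- **That non-significant interactions will be withheld.** The SAP never says so. It makes no commitment to show them.
- **That four separate tests are planned, with a false-positive chance of 19%.** The singular wording fits one overall 2-df test per modifier at least as well, which gives about 10%. Even with four tests, 1 − 0.95⁴ = 18.5% assumes independence, which the shared placebo arm rules out. About 17% is the better figure.
- **That every subgroup effect shown will be exaggerated.** The inflation is an average and concerns the interaction contrast. A single subgroup's effect need not be overstated. In a given trial, overstatement is certain only when the true interaction is below the threshold and the significant estimate has the right sign.

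The published protocol was not available for this review and might fix a pH cut. The conditional reporting sentence is in the SAP itself, so the main point does not depend on that.

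**Conclusion.** The point holds in limited form. Followed as written, the SAP guarantees subgroup results for its two pre-specified modifiers only on a significant interaction, with the alpha, the form of the test and the pH scale left open.

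Under the design SD of about 3.3, equal halves, 90 per arm and alpha 0.05, the filter sits at about 1.9 points. It inflates the reported contrast on average by about 2.5 times for a true 1-point interaction and 1.4 times for a true 2-point one. Power is lower and inflation larger with a larger SD, a stricter alpha or an unequal split; continuous pH would ease both. These figures show the range under stated assumptions and do not predict this trial's results.

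The matter is minor. The primary analysis, the sample size and the main conclusion are not affected.

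**What to change.** Replace the conditional sentence under Subgroup analyses with text that does the following:

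- reports the interaction estimates with 95% intervals and p-values for age and first pH whatever the result;
- uses one joint 2-df test per modifier at a stated alpha;
- uses the stratification cut of 66 years for age, and analyses pH as continuous or at a cut fixed before unblinding. Because the SAP first analyses the arms under codes A, B and C, the cut should precede those coded comparisons too;
- labels these results as exploratory.

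Stratum-specific effects may stay conditional on the interaction test if the authors wish to keep that caution, provided the interaction estimates are always shown.

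The cost is a few sentences in the SAP and one supplementary table, with no new data and no change in sample size. The downside is a few more exploratory estimates to present.

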## Missing data

No missing data is expected for the primary outcome. Missing covariates used for the adjusted analysis will be imputed.

For the secondary outcomes daily and follow-up data is missing from the moment included patients are transferred to an ICU or ward of another hospital. However, questionnaires were still carried out at day 28 and 180, thereby limiting missing data on the outcome mortality. In case patients or their relative could not be reached by phone, follow up data at day 28 and day 180 was missing. Some secondary endpoints are not routinely performed in every ICU, such as the MRC-sum score, CK-MB or NSE.

The number of participants with missing data for baseline variables and other variables used in the analyses will be reported in the manuscript.

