## Secondary outcomes and analyses

The secondary outcomes are summarized in a SPIRIT figure [1].

Dichotomous secondary outcomes include:

- Delirium
  - o CAM-ICU score, ICDSC-score or DOSS-score (yes or no)
- ICU-acquired weakness
  - o Medical Research Council sum score (yes: <48, no: 48-60)
- Need for renal replacement therapy (yes or no)
- At day-28 and day-180:
  - o Survival (yes or no)

Dichotomous variables will be presented as numbers with percentages. For dichotomous variables logistic regression analyses will be carried out. Results will be presented with odds ratios and 95% confidence intervals.

Ordinal secondary outcomes include:

- Renal
  - o Calcium oxalate crystals in urine (negative, few or many)
- At day-28 and day-180:
  - o Functional outcome (mRS scale 0-6)
  - o Neurological outcome (CPC scale 0-5)

Ordinal variables will be presented as numbers with percentages. For ordinal variables a multinomial logistic regression analysis will be carried out. Results will be presented with odds ratios and 95% confidence intervals.

Continuous secondary outcomes include:

- Organ failure:
  - o SOFA-score
- Neurological:
  - o Glasgow Coma Scale
  - Neuron-specific enolase (NSE) ng/mL
  - o The Health Utilities Index-3
- Cardiac/hemodynamics:
  - $\circ$  Troponin ng/L
  - $\circ$  CK U/L
  - $\circ$  CK-MB  $\mu$ g/L
  - Vasopressor duration hours
  - Vasopressor-free days
- Lung:
  - Lung injury score
  - Ventilation duration days
  - Ventilator-free days
- Renal
  - Creatinine clearance μmol/L
  - Oxalic acid (urine) mmol/24h

- Inflammation
  - C-reactive protein mg/L
- Oxidative stress
  - Oxidation-reduction potential (ORP) mV
  - o Antioxidant capacity (AOC)  $\mu$ C
- Pharmacokinetics
  - O Plasma vitamin C concentration μmol/L
- Other clinical outcomes
  - o ICU-stay days
  - Hospital stay days

Continuous variables will be presented as mean with standard deviation or as median with interquartile range when appropriate. Q-Q plots will be assessed visually to check if a given variable follows a normal distribution. For continuous variables linear regression analyses or linear mixed model analyses will be carried out when appropriate. Results will be presented with effect sizes estimates and 95% confidence intervals. When the residuals are not normality distributed the outcome will be transformed before analysis. Analyses will be adjusted for baseline values if applicable.

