Secondary analyses will be performed crude. In an additional analysis, vitamin C groups will be combined and compared to placebo as well to estimate the overall effect of vitamin C.

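### MRC weakness is scored only in patients who are alive, in the study ICU and able to cooperate, so its odds ratio is not a randomised comparison; NSE and CK-MB are also incompletely measured, with no outcome rule

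*SAP*

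**What the plan says.** All three measures are secondary outcomes in the SAP, Section 6, Secondary outcomes and analyses. Weakness is dichotomised as "Medical Research Council sum score (yes: <48, no: 48-60" and analysed by logistic regression with an odds ratio. "Neuron-specific enolase (NSE) ng/mL" and CK-MB are continuous and analysed by linear or linear mixed models. The Framework section applies superiority to secondary outcomes too. The model rule is: "Secondary analyses will be performed crude". Baseline values may be adjusted for, but no site term is named.

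Under Missing data the SAP says: "Some secondary endpoints are not routinely performed in every ICU, such as the MRC-sum score, CK-MB or NSE". The imputation rule covers covariates only: "Missing covariates used for the adjusted analysis will be imputed". The one other safeguard is: "The number of participants with missing data for baseline variables and other variables used in the analyses will be reported in the manuscript". No breakdown by arm or site is stated.

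Three other places bear on who has a value:
- Timing of outcome assessments: nothing was collected on the ward after ICU discharge, although patients discharged in the first four days also had data taken on the discharge day.
- Follow-up and Missing data: most secondary data stop when a patient is transferred to another hospital.
- Table 1: every patient enters with a Glasgow Coma Scale of 8 or less.

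The two planned sensitivity analyses concern death before 96 h and early end of study treatment. Neither deals with untested patients.

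**The concern.** With no rule for a missing outcome, regression uses the patients who have one. Whether that is still a randomised comparison depends on why the others have none, and two causes must be kept apart.

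If an ICU never runs a test, the gap is fixed before allocation and shared by all arms. If a patient has no value because of death, transfer or being unable to take part, the gap arises after allocation and may itself respond to treatment. The tested patients in each arm are then differently selected groups.

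The second cause is built into MRC. The outcome has only yes and no, with no place for patients who died or could not be scored. In patients who all enter comatose, being alive and awake enough to be scored is part of what treatment might change. For NSE and CK-MB the second cause is possible but not documented.

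At stake is how three secondary results are read. A null finding could not be told apart from selective testing. The primary outcome is untouched.

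**Working it through.** The SAP gives no figure for the share tested or for any effect on these endpoints, so there is none to reproduce. The inputs from the SAP are six ICUs, 90 patients per arm as the target, allocation by "computer-generated randomization list in a 1:1:1 ratio to one of the three treatment groups", and "Randomization will be stratified by site and age". All other inputs are assumptions, shown over a range.

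**1. Testing decided by ICU: precision only.** For a 0.5 SD difference at two-sided 0.05, power = Φ(0.5·√(n/2) − 1.96), with n per arm.
- All tested, n = 90: Φ(3.354 − 1.96) = 92%
- 67% tested, n = 60.3: Φ(2.746 − 1.96) = 78%
- 50% tested, n = 45: Φ(2.372 − 1.96) = 66%
- 33% tested, n = 29.7: Φ(1.927 − 1.96) = 49%

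**2. Testing decided by a sharp severity cut-off: closed form.** Severity is normal with SD 1, treatment lowers it by 0.4, and the test is done only above the control median.
- Control mean among tested: φ(0)/0.5 = 0.798, with 50% tested
- Treated mean among tested: −0.4 + 0.3683/0.3446 = 0.669, with 34.5% tested
- Difference 0.129; 0.129/0.40 = 32% kept

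**3. Range for a continuous marker: simulation.** 2,000,000 patients, one pairwise contrast, six sites with severity shifts from −0.5 to +0.5, true effect 0.5 SD on severity. The marker's weight on severity was varied from 0.5 to 1.0, which hardly changed the shares.

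| Who is tested | Tested | Share of true difference kept (crude) |
|---|---|---|
| 3 of 6 sites, everyone there | half of sites | 100% |
| Graded by severity: weak, moderate, strong | 50% | 94%, 81–82%, 61–62% |
| Sharp cut-off | 73%, 50%, 31% | 52%, 37%, 27% |
| 3 milder sites all; 3 sicker sites above a cut-off | 81% | 96–97% |

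The last row is less reassuring than it looks. Take the middle of the three selectively testing sites (shift +0.3, cut-off −0.25).
- Control: 0.3 + 0.3429/0.7088 = 0.784, with 71% tested
- Treated: −0.2 + 0.3984/0.5199 = 0.566, with 52% tested
- Within-site difference 0.2175; 0.2175/0.5 = 43% kept

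The crude figure stays high because fewer treated patients from the sicker sites enter, which pulls the treated mean towards the milder sites. A site term removes that imbalance but not the selection within a site.

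**4. MRC, scored only in less severe patients.** Latent weakness = 0.6·severity + 0.8·noise, weak if above 0.3, with every patient given a latent status.

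| Scored | Treated vs control weak | Risk difference (points) | Odds ratio |
|---|---|---|---|
| Everyone | 27.8% vs 38.5% | −10.7 | exp(−0.487) = 0.61 |
| 3 milder sites, everyone | 21.9% vs 31.7% | −9.8 | exp(−0.507) = 0.60 |
| Less severe 75% | 20.0% vs 24.7% | −4.7 | exp(−0.274) = 0.76 |
| Less severe 59% | 15.2% vs 18.2% | −3.0 | exp(−0.215) = 0.81 |
| Less severe 50% | 12.8% vs 15.1% | −2.3 | exp(−0.194) = 0.82 |

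In the selected rows the risk difference keeps 4.7/10.7 = 44%, 3.0/10.7 = 28% and 2.3/10.7 = 21%. The site-only row differs from the first because those sites are milder; it is still a valid comparison for them.

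**The case against.** The strongest reply is that the SAP's sentence describes differences between ICUs. Site is settled before allocation and is a stratification factor, so such gaps do not select on anything after randomisation. This stands in full: it takes away the general claim about all three endpoints and leaves a loss of precision.

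Second, the SAP nowhere says that NSE was drawn only in patients who had not woken, and it suggests no patient-level trigger for CK-MB. Test schedules are referred to the published protocol and its SPIRIT figure, so their absence here is no fault. This also stands. A reader might infer that selective testing is a fact of this trial, or that it hides most of a real effect. The SAP supports neither. For a marker, losing more than half needs a sharp cut-off with about half or fewer tested; graded selection keeps 61% to 94%. Nor do the MRC calculations support an apparent harm: the effect shrinks but does not change sign.

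Third, the SAP does not count untested patients as not weak, it promises counts of missing data, and neurological benefit is also measured by GCS, HUI-3, mRS and CPC. All true, and this limits the impact. Day-of-discharge data also weaken the part played by early discharge.

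None of this answers the MRC point. Death and transfer are acknowledged in the SAP, and the yes/no analysis makes no provision for them.

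**Conclusion.** The concern holds in a limited form. For MRC, the planned odds ratio compares tested survivors, a group formed after randomisation, and no stated analysis deals with the rest. Death and transfer come from the SAP; the need for a cooperative patient is my assumption about how the score is taken. In the scenarios run, 21% to 44% of a 10.7-point risk difference remains, but those inputs are assumed and the true shares are unknown.

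For NSE and CK-MB the defect is an unspecified rule, not a demonstrated bias. If testing varied by ICU alone, the contrast is sound and only power falls, for example from 92% to 66% with half tested. If testing within an ICU followed the patient's condition, the share kept could fall to about 27% in the extreme case. The SAP does not say which applies. The case is weakest for CK-MB, where no mechanism is suggested.

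The change is worth making because it is cheap. It does not affect the primary conclusion.

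**What to change.** Amend the SAP while the data are still coded A, B and C:

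1. **MRC.** Tabulate by arm four categories: weak, not weak, alive but not tested, and dead. State that untested patients are not counted as not weak. Keep the odds ratio, but describe it as conditional on being a tested survivor.
2. **All three endpoints.** Report the share tested by arm and by site, and include site in the model, since randomisation was stratified by it. Say that this corrects for site mix only and does not repair selection within an ICU.
3. **Sensitivity analysis.** Repeat each comparison in sites that tested routinely, with the coverage threshold fixed before unblinding. This should not be the main analysis: it drops data, any threshold is a judgement, and it still depends on patients being in the ICU.
4. **Label** the three comparisons exploratory.

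The cost is some SAP wording, one coverage table and a few extra model runs. Intervals will be wider in the restricted analysis. No new data are needed.
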